PI Principal Investigator
PRP Platelet rich plasma
RP Radical Prostatectomy

PSA Prostate-Specific Antigen

SAE Serious Adverse Event/Serious Adverse Experience

SHIM Sexual Health Inventory for Men SOP Standard Operating Procedure

Study Summary

Title	A Study Evaluating Intraoperative Application of Platelet-Rich Plasma to the Neurovascular Bundles During Nerve-Sparing Radical Prostatectomy: Initial Technical Description and Prospective Early Postoperative Outcomes Analysis					
Running Title	PRP Application During RP					
Protocol Number	16-001320					
Methodology	Open label					
Overall Study Duration	18 months					
Subject Participation Duration	18 months					
Single or Multi-Site	Single site					
Objectives	To evaluate the safety, tolerability, feasibility and efficacy of using platelet rich plasma to facilitate early nerve healing and decrease erectile dysfunction after nerve-sparing radical prostatectomy.					
Number of Subjects	20					
Diagnosis and Main Inclusion Criteria	Post-surgical erectile and urinary dysfunction. Main inclusion criteria are men, aged 50-60 years, with normal sexual function and regular sexual partner, undergoing RP for newly diagnosed prostatic adenocarcinoma.					
Study Product, Dose, Route, Regimen	Autologous Platelet-Rich Plasma The dose is approximately 1,000,000 platelets/mL and the product is applied topically to the neurovascular bundle once during radical prostatectomy					
Duration of Administration	One time drug administration with duration of drug application is approximately 4 hours.					
Reference therapy	None					
Statistical Methodology	The safety evaluation will focus on the number of adverse events including local reactions, expected serious adverse events and unexpected serious adverse events. All events will be collected, recorded and assessed for severity as a means to facilitate the reporting process. All patients will undergo an assessment of sexual and urinary function and oncologic outcomes at 3, 6, 9, 12 and 18 months after surgery. All patients will be evaluated for perioperative complications, length of stay, and need for blood transfusion.					

Version 4.0

1 Introduction

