4.4 Early Withdrawal of Subjects

4.4.1 When and How to Withdraw Subjects

A subject may withdraw at any time prior to RP. There are no adverse safety considerations in the study for those deciding to withdraw from the study. Subjects may choose to discontinue study participation after RP surgery and will be counted as withdrawn

A subject consenting to the study will receive PRP at the time of RP unless the surgical team decides intra-operatively to withdraw a subject from the study in the following situations:

- Estimated blood loss greater than 750 mL
- Evidence of disease grossly and/or pathologically that the prostate cancer is locally advanced or metastatic

• Documentation of the reason for withdrawal will be retained in the study files.

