4.4.2 Data Collection and Follow-up for Withdrawn Subjects

As part of normal clinical care, subjects that have withdrawn from the study will still have routine postoperative monitoring after RP. Any collected study data from withdrawn subjects will not be included in the data analysis. Since all patients have their outcomes tracked after RP at Mayo Clinic, postoperative data would be available should this be needed as part of another study protocol.

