4.4.3 Replacement of Subjects

If subjects withdraw from the study, they will be removed from the final study cohort. In the situation of a subject withdrawing from the study, we will continue to recruit subjects such that 20 total subjects complete the entire study with 18 months of follow-up.

5 Study Drug

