7.3 Subject Population(s) for Analysis

Data from all subjects consented for the study and completing postoperative visits will be evaluated.

² Vitals will be abstracted from the medical record for visit 3, post-operative day 2

³ Week 1 and week 12 visits may be done on-site or via telephone interview or email. Physical exam and vitals will be performed for these visits if participant is able to return to Mayo Clinic. Outside records for physical exam and vitals will be requested if visits are done remotely.

⁴ The 6, 9, 12 and 18 Month visits may be done remotely via telephone interview or email. Completed SHIM/EPIC Questionnaires may be returned to study site by mail, email or fax. PSA testing: A local clinic may be used for venipuncture, using mail in lab kit for sample return to Mayo Clinic. PSA testing window for week 12 and 6, 9, 12, 18 month visit is +/- 21d

8 Safety and Adverse Events

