8.2 Recording of Adverse Events

At each contact with the subject, the study team must seek information on AE by specific questioning and, as appropriate, by examination. Information on all adverse events should be recorded immediately in the source document, and also in the appropriate AE section of an electronic adverse event worksheet. All clearly related signs, symptoms, and abnormal diagnostic, laboratory or procedure results should recorded in the document.

All adverse events occurring during the study period must be recorded. The clinical course of each event should be followed until resolution, stabilization, or until it has been ultimately determined that the study treatment or participation is not the probable cause. Serious adverse

events that are still ongoing at the end of the study period must be followed up, to determine the final outcome. Any serious AE that occurs after the study period and is considered to be at least possibly related to the study treatment or study participation should be recorded and reported immediately.

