9.1 Confidentiality

Information about study subjects will be kept confidential and managed according to the requirements of HIPAA. Those regulations require a signed subject authorization informing the subject of the following:

- What PHI will be collected from subjects in this study
- Who will have access to that information and why

- Who will use or disclose that information
- The rights of a research subject to revoke their authorization for use of their PHI. In the event that a subject revokes authorization to collect or use PHI, the investigator, by regulation, retains the ability to use all information collected prior to the revocation of subject authorization. For subjects that have revoked authorization to collect or use PHI, attempts should be made to obtain permission to collect at least vital status (long term survival status that the subject is alive) at the end of their scheduled study period.

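### Men who receive PRP and then withdraw are dropped from the primary safety analysis and replaced, and no all-treated safety set is defined

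*Combined protocol and SAP*

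**What the plan says.** Sections 2 and 3.2 make safety and tolerability of PRP the primary objective. PRP is applied once, during the prostatectomy (sections 5.2 and 5.4.1).

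Four provisions decide who is analysed:

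- Section 4.4.1, on leaving after surgery: "Subjects may choose to discontinue study participation after RP surgery and will be counted as withdrawn".
- Section 4.4.2, on their data: "Any collected study data from withdrawn subjects will not be included in the data analysis".
- Section 4.4.3, on the cohort: "If subjects withdraw from the study, they will be removed from the final study cohort". It adds that "we will continue to recruit subjects such that 20 total subjects complete the entire study with 18 months of follow-up".
- Section 7.3, the only analysis population: "Data from all subjects consented for the study and completing postoperative visits will be evaluated". It does not say which visits, or how many, must be completed.

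Other text concerns collection. The Statistical Methodology row of the Study Summary says "All events will be collected, recorded and assessed for severity as a means to facilitate the reporting process", and section 8.2 says "All adverse events occurring during the study period must be recorded". Section 9.1 notes that, even when a subject revokes authorization, the investigator "retains the ability to use all information collected prior to the revocation of subject authorization".

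**The concern.** A man who leaves after surgery has normally already been exposed to the whole of the study treatment. His later decision to stop cannot undo that exposure, yet the plan removes both his events and his place in the denominator, then recruits someone else. The analysed group is therefore chosen by something that happens after treatment.

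If men with complications are more likely to leave the study, the reported event rate will be lower than the rate among the men exposed. If leaving is unrelated to events, no bias is expected, but known events and exposed men are still lost from a trial of about 20.

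The design gives little protection against this. There is no randomized control and section 8.5 sets no stopping rule. Sections 3.1 and 8.6 compare safety with registry patients, for whom no matching 18-month completion rule is stated. Section 1.5 raises a possible effect on cancer recurrence, and PSA is followed to 18 months, so late withdrawals could matter as well as early ones.

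**Working it through.** **Reading the rules together.** Take a man who receives PRP, has an adverse event and stops at month 4.

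1. Section 8.2 has his event recorded.
2. Section 4.4.1 counts him as withdrawn.
3. Section 4.4.2 leaves out everything collected on him, with no exception for treated men or for safety data.
4. Section 4.4.3 takes him out of the cohort and adds a replacement.
5. Section 7.3 offers no other analysis set in which he could appear.

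His event is on file but not in the primary analysis.

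**Inputs for the size.** From the documents: 20 completers (section 4.4.3). Section 7.1 gives no event rate, precision target or withdrawal rate, so there is no stated figure to reproduce. Everything below except the 20 is an assumption.

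**How often the rule would operate.** Let *d* be the chance that a treated man withdraws, independently of the others. No treated man is removed only if the first 20 treated all complete, so P(at least one removed) = 1 − (1 − *d*)^20. The expected number removed before 20 complete is 20*d*/(1 − *d*).

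| *d* | P(at least one removed) | Expected number removed |
|---|---|---|
| 2% | 33.2% | 0.4 |
| 5% | 64.2% | 1.1 |
| 10% | 87.8% | 2.2 |
| 20% | 98.8% | 5.0 |

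**What one or two removals do.** Exact (Clopper-Pearson) 95% intervals, where every removed man had an event and no completer did:

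| Removed | All treated | Completers only |
|---|---|---|
| 1 | 1/21 = 4.8% (0.1% to 23.8%) | 0/20 = 0% (0% to 16.8%) |
| 2 | 2/22 = 9.1% (1.1% to 29.2%) | 0/20 = 0% (0% to 16.8%) |

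If the removed men had no events, only precision is lost: the upper limit would be 16.1% for 0/21 or 13.7% for 0/25, against 16.8% for 0/20.

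**Expected bias.** Let *p* be the true event rate, and *w1* and *w0* the withdrawal chances with and without an event. The expected rate among completers is *p*(1 − *w1*) / [*p*(1 − *w1*) + (1 − *p*)(1 − *w0*)]. With *p* = 10% and *w0* = 5%:

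- *w1* = 5%: 0.095/0.950 = 10.0%
- *w1* = 20%: 0.080/0.935 = 8.6%
- *w1* = 50%: 0.050/0.905 = 5.5%

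**The case against.** The strongest reply is that safety information is not lost. All events are recorded (8.2), unresolved events are followed (8.1), serious ones go to the IRB and FDA (8.3), and the number and type of serious events are reviewed regularly (8.6). None of this is limited to completers. The Study Summary also says that every patient will be evaluated for complications around surgery, length of stay and transfusion, which is a statement about evaluation and not only collection.

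This stands in part. The loss is from the analysis, not from recording, reporting or oversight. But none of these sections names an analysis set or overrides the explicit exclusion in 4.4.2. At most, the Study Summary sentence conflicts with 4.4.2, which would itself need resolving. Privacy does not force the exclusion either, given section 9.1.

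A second reply is that nothing in the documents links complications to withdrawal. Missed visits are handled separately by contacting the subject (7.2 and 9.4), and visits from week 1 may be remote. That is right: the direction and size of any bias are assumed. The higher rates used above (20% withdrawal overall, 50% after an event) have no basis in the documents. The shift from 10.0% to 8.6% is about 0.3 of an event in 20 men (20 × 0.014), the intervals for 0/20 and 1/21 overlap heavily, and the plan has no test whose result could change. These points limit the likely consequence. They do not alter what the rules do to an exposed man's data.

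**Conclusion.** The concern holds. As written, sections 4.4.1 to 4.4.3 and 7.3 remove treated men who withdraw, together with any adverse events, from the analysis of the primary objective, and no other text restores them. This is a stated rule that produces the wrong safety set, not a missing detail.

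The textual conclusion needs no assumption. The size does. It ranges from nothing, if no treated man withdraws, to roughly a halving of a 10% event rate (to 5.5%) in the most extreme case examined, where half the men with events withdraw against 5% of the others. In so small a trial, one or two removals can turn a non-zero event count into zero. It should be corrected because it bears on the primary objective and costs little to put right.

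**What to change.** Amend sections 4.4.2, 4.4.3 and 7.3 to say that:

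- every man who received PRP is in the safety analysis, with his data up to his last contact;
- a replacement is added to the men already treated and does not take the place of the man who withdrew;
- the 20 men completing 18 months remain the set for 18-month sexual and urinary function;
- the numbers treated, withdrawn and replaced are reported, with reasons.

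A sensible extension is to report separately any man who had the 180 mL study blood draw but was withdrawn during surgery before PRP, because section 1.5 names the draw as a study risk.

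The cost is a few lines of text. No visit or test is added, because adverse events are already assessed from surgery onward (section 6.8). The safety denominator may exceed 20.

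As a separate matter of clarity that does not affect this conclusion, the post-operative aspirin and heparin wording could be aligned in the same amendment. Section 4.2 excludes a need lasting 2 weeks or more, while section 5.6 can be read as barring any use in the first 2 weeks. The permitted duration is for the clinical team. Later use should be recorded as a concomitant medication or deviation, not treated as a reason for removal.

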4.4.3 Replacement of Subjects

If subjects withdraw from the study, they will be removed from the final study cohort. In the situation of a subject withdrawing from the study, we will continue to recruit subjects such that 20 total subjects complete the entire study with 18 months of follow-up.

5 Study Drug

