3.3 Secondary Study Endpoints

Secondary Objective(s):

- To assess the feasibility of applying 1 dose of PRP intra-operatively at the time of bilateral nerve-sparing RP in 20 men with prostatic adenocarcinoma.
- To assess preliminary clinical benefit/efficacy of using PRP in facilitating early nerve healing and decreasing ED at 3, 6, 9, 12 and 18 months after nerve-sparing RP.
- To assess change in urological function by measuring urinary continence before and at 3, 6, 9, 12 and 18 months after PRP treatment during nerve sparing surgery.

4 Subject Selection Enrollment and Withdrawal

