7.1 Sample Size Determination

For the proposed trial, a sample of 20 subjects is proposed. This sample will permit a statistical description of that is required for the primary and secondary objectives. Use of 20 subjects is in the range normally enrolled for trials of this nature.

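### Feasibility has no defined measure, and men withdrawn at surgery are removed and replaced, so the listed reasons for not applying PRP drop out of the denominator

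*Combined protocol and SAP*

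**What the plan says.** Section 3.3 lists the objective as "To assess the feasibility of applying 1 dose of PRP intra-operatively at the time of bilateral nerve-sparing RP in 20 men with prostatic adenocarcinoma". Neither 3.3 nor 7.2 says what is counted, over whom, or what result would count as feasible.

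Section 4.4.1 says that a consenting man receives PRP "unless the surgical team decides intra-operatively to withdraw a subject from the study". It gives two reasons: estimated blood loss above 750 mL, and locally advanced or metastatic disease. Both also stand as exclusion criteria in 4.2.

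Section 4.4.2 then says: "Any collected study data from withdrawn subjects will not be included in the data analysis". Section 4.4.3 takes withdrawn men out of the final cohort and adds that "we will continue to recruit subjects such that 20 total subjects complete the entire study with 18 months of follow-up". Section 7.3 limits the evaluated data to consented men who complete postoperative visits.

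Reasons for withdrawal are kept on file (4.4.1), as is a screening and enrollment log (6.1). No section plans to report either as the feasibility result.

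**The concern.** A feasibility result is informative only if failures can appear in it. Here the cohort is selected partly on the outcome: a man in whom PRP is not applied for either listed reason is removed and another man takes his place. The final group of 20 would look the same whether 20 or 30 men had to be taken to surgery to produce it. A reader planning a larger trial would learn little about how many consented men can actually receive the product.

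The same rule touches the primary safety objective. Section 5.4.1 has 180 mL of blood drawn during the operation, while PRP goes on only after the anastomosis and hemostasis. A man could give study blood and then be withdrawn. Section 1.5 names hypotension and possible transfusion as risks of that draw, yet under 4.4.2 his data would not be analysed.

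**Working it through.** **The plan's own figure.** Section 7.1 says "For the proposed trial, a sample of 20 subjects is proposed" and supports this with "Use of 20 subjects is in the range normally enrolled for trials of this nature". No rate, precision target, alpha or power lies behind it, so there is nothing to recompute. What can be checked is how the denominator is formed.

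**Tracing the denominator.**

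1. A man consents and goes to RP.
2. He receives PRP, or is withdrawn at surgery for one of two listed reasons (4.4.1).
3. If withdrawn, his data are not analysed (4.4.2) and he leaves the cohort (4.4.3).
4. A replacement is recruited, until 20 men complete 18 months (4.4.3).
5. Section 7.3 does not bring the withdrawn man back.

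So both listed reasons for non-application are removed before any proportion is formed.

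**Size, for illustration.** Let k be the number of consented men withdrawn at surgery without PRP. The documents give no rate, so k is assumed. Assume also that nobody leaves after receiving PRP and that there is no technical failure. The proportion over all consented men starting RP is 20/(20 + k). The exact (Clopper-Pearson) 95% limits for x out of n are the 2.5% quantile of Beta(x, n − x + 1) and the 97.5% quantile of Beta(x + 1, n − x). When x = n the upper limit is 1 and the lower is 0.025^(1/n), so for 20/20 it is 0.025^(1/20) = 0.832.

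| k (assumed) | Over all men starting RP | Exact 95% CI | Under the written rule |
|---|---|---|---|
| 0 | 20/20 = 100% | 83.2 to 100 | 20/20 |
| 1 | 20/21 = 95.2% | 76.2 to 99.9 | 20/20 |
| 2 | 20/22 = 90.9% | 70.8 to 98.9 | 20/20 |
| 5 | 20/25 = 80.0% | 59.3 to 93.2 | 20/20 |
| 10 | 20/30 = 66.7% | 47.2 to 82.7 | 20/20 |

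**How surprising 20/20 would otherwise be.** If each man had probability d of not receiving PRP, the chance that 20 consecutive men all receive it is (1 − d)^20. For assumed d of 5%, 10% and 20% this is 0.95^20 = 35.8%, 0.90^20 = 12.2% and 0.80^20 = 1.2%. When all non-application is by the listed withdrawals, the written rule gives 20/20 in each case.

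**Men who leave after PRP.** Sections 4.4.1 and 4.4.3 also remove and replace these men, but for feasibility they are successes. With m of them the proportion is (20 + m)/(20 + m + k). With k = 2 and m = 3 (assumed) it is 23/25 = 92.0%, not 20/25 = 80.0%. The table must therefore not be read with k as the total number replaced.

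**Technical failure.** A failed draw, a device fault, a platelet ratio below the 5.4 check of 2, or incomplete application is not a listed reason for withdrawal. If one such man were kept and followed, 7.3 would admit him and the result would be 19/20 = 95.0% (75.1 to 99.9).

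**The case against.** The strongest reply is that both listed reasons are exclusion criteria in 4.2. On that view the men are late eligibility failures, and feasibility means technical success in men still eligible when PRP is due. Under that definition, leaving them out is not a bias. This stands in part: the protocol does not say which definition it means, and the two kinds of non-application should not be pooled without distinction. But these reasons become known only after consent and at surgery, so they bear on how often PRP can be delivered to men planned for it. Both proportions are worth reporting.

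A reader might infer that the plan can never return anything but 100%. The documents do not support that. They are silent on technical failures, and such a man, if retained, would lower the figure.

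A reader might also infer that harm from the blood draw in withdrawn men would go unseen. That goes too far. Section 8.2 requires all adverse events in the study period to be recorded, and 8.3 sets out reporting to the IRB and FDA. Section 5.4.1 also does not fix whether the draw comes before or after the withdrawal decision. What remains is that 4.4.2 keeps such a man out of the analysed safety data if his blood was drawn first.

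Finally, the study is small and descriptive, and the retained records would allow the full denominator to be rebuilt. That lowers the severity, but no section plans to use those records and 4.4.2 excludes withdrawn men's data from analysis.

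**Conclusion.** The point holds, as a should-fix. Feasibility is undefined, and a stated rule removes and replaces men in whom PRP is not applied for either listed reason. As an estimate of deliverability in consented men taken to RP, the result is biased upward, to 20/20 unless a technical failure is retained. The gap is about 9 percentage points with 2 such withdrawals (100 − 90.9) and 20 points with 5 (100 − 80.0). These sizes rest on assumed counts and on nobody leaving after PRP; the documents give no rate. The safety consequence is conditional on blood having been drawn before withdrawal, and concerns analysis rather than recording.

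It is not a must-fix: the objective is secondary and descriptive, no test depends on it, and the needed records are already kept.

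**What to change.** Amend 3.3, 4.4.2, 4.4.3, 7.2 and 7.3 as follows.

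- **Measure.** Men whose PRP met the 5.4 check and was applied to both bundles, divided by all consented men who start RP, with an exact 95% CI.
- **Reasons.** List every non-application by reason, separating ineligibility found during surgery from technical failure. Also give the proportion among men still eligible at the time of application.
- **Men who leave after PRP.** Keep them in the feasibility denominator, and in the numerator as men who received qualifying PRP.
- **Safety set.** Include every man who had study blood drawn or PRP applied, whether or not he was later withdrawn or replaced.
- **Replacement.** It may continue for the 18-month outcome cohort. No withdrawal criterion changes.

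The cost is wording and a short table, drawing largely on the withdrawal files and enrollment log already kept. The drawback for the sponsor is that reported feasibility may look less favourable.
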